We conducted a study that showed ethnic disparity in use of psychotherapy offered in primary care for African American older adults with depression. We capitalized on depression screening and clinical diagnostic assessments that occurred in PROSPECT.(25, 26) We focused on the 582 persons with complete data assessed at baseline.(27) Compared to White older adults, persons who self-identified as African-American were less likely to have received Interpersonal Psychotherapy if they had minor depression even after adjusting for potentially influential covariates (AOR)=0.22, 95% confidence interval (CI)=0.06-0.80). African Americans were less likely to receive psychotherapy than Whites among persons who met criteria for major depression as well. While the intervention “raised all boats,” the ethnic disparity persisted even in the intervention practices. Focus on the clinical setting may improve health but not health disparities. A model that is accessible in the community and linked to clinics may be more effective in mitigating health disparities over clinical approaches alone.

We developed a peer intervention and evaluated the feasibility and acceptability of peer mentors for older adults and examined client and peer experiences of the program. We found that engagement was high (90% percent of older adults attended all 8 meetings with the peer). The majority was African American older adults (74%) and 85% had decrease in PHQ-9 scores [Mean 7.1 (SD 7.1) p-value < 0.001].(28) Loneliness decreased (pre-study mean 36.7 ± 5.4 ; post-study mean 31.4 ± 16.7 , p-value 0.03) and coping skills increased (pre-study mean 65.6 ± 13.2 , post-study mean 69.9 ± 10.4 , p-value 0.006). Older adults emphasized the importance of a trusting relationship, credibility of the peer and usefulness of professional supervision in the program. Participants described benefits such as hope, changes in attitude, behavior and insight. The program also successfully connected older adults to community and clinical resources during and after the study.

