We successfully contacted 85% of patients at 12 months and assessed depression with the PHQ-9 by telephone. Sixty-eight percent of patients had PHQ-9 scores that remained below baseline scores by 5 points or more. After completion of the feasibility study, we recruited 27 additional participants (total of 57 older adults) seeking to obtain greater experience with a larger sample of peers and older adults to refine the peer program. We tried telephone delivery of the program for two participants. Although peers found the telephone convenient, relationship building was more difficult, and two older adults missed telephone calls more frequently but attended in-person meetings regularly. Given the importance of problems of loneliness among our study participants, we continued with in-person meetings and used telephone calls infrequently when peers were unable to meet in person due to weather. We concluded that use of supervised peer mentors is a promising model of depression care delivery for older adults. We conducted an analysis using data from 57 older adults in the pilot study to assess whether self-efficacy predicted change in depression. We found that improvement in self-efficacy was associated with a decline in depression.

We studied peer mentor communication that would inform peer training and role development. Our aim was to describe and associate communication behaviors used by supervised peer mentors with working alliance and depression.(29) We used the Roter Interaction Analysis System, a quantitative method to analyze health communication between peers and older adults in the pilot study. We looked at a variety of communication behaviors similar to other studies on communication behaviors in mental health. (30, 31) We found that peers used a variety of skills learned in training. This included client-centered talk, positive rapport building, emotional responsiveness, and education and counseling (see Table 1). Specific communication behaviors such as emotionally responsive talk and education about psychosocial topics were associated with decreased depression (all $p < .001$). We concluded that trained peer mentors can use skilled communication behaviors that is client-centered to provide depression care services to older adults.

4. Study Procedures

- a. Study design, including the sequence and timing of study procedures (distinguish research procedures from those that are part of routine care).

Study flow

- Screen by telephone

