Primary analyses will be intention-to-treat. Descriptive statistics (e.g. frequencies, means, standard deviations, medians, interquartile ranges) and graphic displays will be generated for all study variables to ensure that distributional and other assumptions of the planned analyses are met. We will minimize missing data using our team's documented retention strategies that have resulted in only 14% attrition.³⁷ All primary analyses will be adjusted for sex, demographic factors, life events, medical comorbidity, and use of mental health services. Hypothesis tests will be two-sided with $\alpha=0.05$.

c. Statistical plan including sample size justification and interim data analysis.

Table 3. Assessment schedule														
Variable	Measure	Timing of assessments												
		0 wk	1 wk	2 wk	3 wk	4 wk	5 wk	6 wk	7 wk	8 wk	3 mth	6 mth	9 mth	12 mth
Sociodemographic factors	Self-report	x												
Depression (self-report)	PHQ-9	x	x	x	x	x	x	x	x	x	x	x	x	x
Depression (assessed by clinician)	Mini-International Neuropsychiatric Interview (MINI)	x								x	x	x	x	x
Client engagement	At least 80% attendance of meetings, peer logs of meetings	x	x	x	x	x	x	x	x	x				
Client engagement	Working Alliance Inventory-SR	x	x	x	x	x	x	x	x	x				
Physical, social and emotional function	Medical Outcomes Study Short Form 36	x								x	x	x	x	x
Self-efficacy	General Self Efficacy Scale	x	x	x	x	x	x	x	x	x		x		x
Loneliness	R-UCLA Loneliness Scale	x	x	x	x	x	x	x	x	x		x		x
Coping skills	Brief Copie	x								x	x	x	x	x
Medical comorbidity	WHO WMH CIDI	x								x	x	x	x	x
Clinical and community health service use	Cornell Service Index	x								x	x	x	x	x
New uptake of counseling and antidepressant	Self-report	x	x	x	x	x	x	x	x	x				
Social determinants of Health	Accountable Health Communities Core Health-Related Social Needs Screening Questions	x								x	x	x	x	x

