Our primary study aim is to test the effects of the Peer Enhanced Depression Care Program for reducing depressive symptoms compared to Enhanced Usual Care. H1: Older adults randomized to the Peer Program (vs. control) will report decreased depression (PHQ-9 score decrease ≥ 5) at 8 weeks, 3, 6, 9 and 12 months. To assess the immediate effects of treatment, we will fit a mixed effects model(59) with nested random effects for counselor and participant such that $E[y_{ij}] = \beta_0 + \beta_1 tx + \beta_2 week + \beta_3 tx * week$, adjusted for sex and other covariates (see 7.a.), where y_{ij} is the PHQ9 score for the i th individual at intervention week j , β_2 is the rate of change in PHQ-9 for individuals randomized to EUC, and β_3 , the coefficient of interest, is the difference in rates of change in PHQ-9 between the Peer Program and Enhanced Usual Care study arms. To assess durability of the intervention effects, we will model PHQ-9 at each post-intervention follow-up (months 3,6,9 and 12) using a time-averaged model, which adjusts for PHQ-9 at week 8 and models PHQ-9 scores at later time points as a function of treatment assignment.

Sample size and power

We calculated power to detect a difference in rate of PHQ-9 decline over the 8-week intervention period via simulation. Assuming 20% attrition, design effect of 1.2 (to account for clustering within peers (62) based on ICCs from pilot data), and regression parameters from our preliminary data (SD of random intercept: 2.83; SD of random errors: 0.11), with N=160, we would have 99% power to detect a difference in slope of 0.625, which corresponds to a between-group difference of 5 points on the PHQ-9 at 8 weeks. Similarly, we calculated power to detect a sustained post-intervention between-group difference. We will have 99% power to detect a sustained 5-point difference in PHQ-9 during that period.

Data and safety monitoring plan

We will have a Data and Safety Monitoring Board (DSMB) to monitor the study with an attendant monitoring plan that will involve interim analysis. We will provide descriptive data for the first 6 months after the first participant has enrolled in the study to review both the non-serious and serious adverse event rates. We will meet every 6 months and also meet on an ad hoc basis if the real time serious adverse events warrant meeting, in their judgment.

d. Early stopping rules.

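### The 99% power claim for N=160 rests on a residual SD of 0.11, which is too small for a whole-number PHQ-9 score and does not fit the pilot's spread of change

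*Combined protocol and SAP*

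**What the plan says.** Section 6.c (Sample size and power) describes a simulation for the difference in rate of PHQ-9 decline over the 8 intervention weeks. It assumes 20% attrition, a design effect of 1.2 for clustering within peers, and variance parameters from preliminary data: "SD of random intercept: 2.83; SD of random errors: 0.11". The result is "with N=160, we would have 99% power to detect a difference in slope of 0.625", which the plan equates with 5 points at 8 weeks. A second claim, for the follow-up period, comes with no variance inputs of its own: "We will have 99% power to detect a sustained 5-point difference in PHQ-9 during that period".

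On the analysis model, section 6.c says "we will fit a mixed effects model(59) with nested random effects for counselor and participant". Neither the model nor the list of inputs mentions a random slope.

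Section 3 (Background) gives the pilot result: "85% had decrease in PHQ-9 scores [Mean 7.1 (SD 7.1) p-value < 0.001".

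**The concern.** A residual SD of 0.11 means that each participant's weekly scores lie almost exactly on a straight line. With no slope SD, it also means that everyone in an arm follows the same slope. Neither is believable for a 0 to 27 symptom scale scored in whole points, and the pilot shows wide variation in change between people.

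This paragraph is the only justification of N=160 in the document. If a key variance input is unusable, the reported power says nothing about what the trial can detect. A reader could not judge a null or small result against it.

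**Working it through.** **Inputs.** Two-sided alpha 0.05 (section 6.b); N=160, 20% attrition, design effect 1.2, slope difference 0.625 per week, intercept SD 2.83 and residual SD 0.11 (section 6.c); 1:1 allocation (section 4, Randomization procedures); weekly PHQ-9 at weeks 0 to 8 (Table 3); pilot decrease 7.1, SD 7.1, 85% improving (section 3).

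Effective number per arm = 80 × 0.8 / 1.2 = 53.3. Sum of squares of weeks 0 to 8 about their mean = 60.

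**1. The plan's own figure.** With a common slope, the SE of the slope difference = (0.11/√60) × √(2/53.3) = 0.00275, so 0.625/0.00275 ≈ 227 standard errors. Power is effectively 100%. The 99% is reproduced only in the sense that power is saturated. The 8-week difference with 99% power would be 8 × 0.00275 × 4.286 = 0.094 points.

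**2. Whole-number check.** If fractional positions are spread evenly, rounding has an SD of 1/√12 = 0.289. Taking the nearest whole numbers to a line over weeks 0 to 8, with the most favourable intercept, the root-mean-square miss is at least 0.27 at 0.625 per week and 0.285 at the pilot's 7.1/8 = 0.89 per week. An SD of 0.11 is below rounding error alone. It could occur only if scores stayed flat or moved by exact whole points each week, and neither slope does that.

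**3. Pilot check on the SD.** The listed inputs imply:
- within-person correlation = 2.83²/(2.83² + 0.11²) = 0.998;
- SD of 8-week change = √2 × 0.11 = 0.156.

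Read as the SD of change, the pilot's 7.1 is 7.1/0.156 ≈ 46 times larger.

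**4. Pilot check that does not use the SD.** With a change SD of 0.16, a mean drop of 7.1 means that every participant improves, but the pilot reports 85%. Under normality, z(0.85) = 1.036, so the change SD must be 7.1/1.036 = 6.85. If 7.1 is the mean among improvers only, it is 7.1/(1.036 + 0.233/0.85) = 5.42. Conversely, a normal distribution with mean 7.1 and SD 7.1 has 84% improving, which supports reading 7.1 as the SD of change.

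**5. Other readings of 0.11.**
- As a variance: SD 0.332, change SD 0.469, still 15 times below 7.1.
- As a slope SD: the residual SD is then missing.
- As a slope SD with 2.83 as the residual SD: change SD = √(2 × 2.83² + 64 × 0.11²) = 4.1, still below the 5.4 to 7.1 that the pilot needs.

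**6. Power with a usable spread.** Change variance = 2 × residual variance + 64 × slope variance. SE of the 8-week difference = 8 × √((residual variance/60 + slope variance) × 2/53.3). With the change variance set to 7.1² = 50.41:

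| Split of change variance | Residual SD | Slope SD | SE (points) | Power for 5 points | Difference at 80% power |
|---|---|---|---|---|---|
| All slope | 0 | 0.89 | 1.375 | 95.3% | 3.85 |
| Half and half | 3.55 | 0.63 | 1.204 | 98.6% | 3.37 |
| All residual | 5.02 | 0 | 1.004 | 99.9% | 2.81 |

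Sensitivity:
- Change SD 5.4: 99.8% to over 99.9% (2.9 to 2.1 points at 80% power).
- Change SD 8 (assumed): 89.8% to 99.3% (4.3 to 3.2 points).
- Only weeks 1 to 8 in the model (sum of squares 42), change SD 7.1: 95.3% to 98.6%.
- Target of 3 points, change SD 7.1: 59% to 85%.

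A simulation of 20,000 trials with 10 peers in the intervention arm only, an ICC of 0.037 (back-solved from the design effect of 1.2) and Satterthwaite degrees of freedom gave 95.2%, 98.5% and 99.9% for the three rows. If the test instead used a t reference with 9 to 18 degrees of freedom (an assumption), the all-slope case would fall to about 90% to 93%.

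**The case against.** The strongest reply is that the conclusion barely moves. If the random effects are intercepts only and the pilot spread is all weekly residual, power is 99.9% and the stated 99% survives. At a change SD of 5.4 it survives under every split. At a change SD of 7.1 or less, getting below 99% takes a between-person slope SD that the documents never give, or a model restricted to weeks 1 to 8. This stands as a limit on the consequence. It does not rescue the calculation, because the split is unknown. If slopes do vary, an intercept-only analysis would also understate the standard error: in one simulated case (residual SD 2, slope SD 0.81) the type I error was about 33%.

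Second, the simulation may have included a slope SD that the text omits. A value near 0.89 would absorb both pilot checks, so the figures 0.998, 0.16 and 46-fold hold only if nothing was left out. The rounding check is unaffected, since it concerns scatter around each person's own line.

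Third, the labels may have been swapped (2.83 residual, 0.11 slope). That passes the rounding check and gives over 99.9% power, but its change SD of 4.1 still falls short of the pilot.

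Fourth, the pilot is a weak anchor. The text does not state outright that 7.1 is the SD of change. The feasibility sample appears to be 57 − 27 = 30 people, for which an SD of 7.1 has a 95% interval of about 5.7 to 9.5. The pilot was also mainly in person, while the trial is by telephone. This is a good reason to report a range, but no value in that interval is near 0.16.

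Finally, the plan's arithmetic is not wrong given its inputs. That is so: the fault lies in an input.

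**Conclusion.** The concern holds. As labelled, 0.11 cannot be the residual SD of weekly PHQ-9 totals at the slopes that the plan states. Taken with the other listed inputs, it also contradicts the pilot that it is said to come from. The 99% is therefore unsupported, although it may turn out to be true.

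If the change SD is 7.1, with the plan's attrition and design effect, power for 5 points is 95.3% to 99.9%. If the SD is 8 (assumed), it is 89.8% to 99.3%. These figures rest on normality, linear change over weeks 0 to 8, and reading 7.1 as the SD of within-person change. The low end is not a strict floor if few-cluster critical values are used. Because the slope/residual split is not given, no single corrected power can be stated. N=160 is not shown to be too small for the 5-point target.

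**What to change.** In section 6.c:

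- State what 0.11 is and correct it.
- Estimate the residual SD and the between-person slope SD from the pilot's weekly PHQ-9 data, and list both.
- Rerun the simulation under the model that will be fitted, with peer clustering in the intervention arm, and replace the 99% with the result. Say whether that model has a random slope.
- List the variance inputs for the sustained-difference claim and recheck its 99%.
- Add the difference detectable with 80% power at N=160 (about 2.8 to 3.9 points if the change SD is 7.1).

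The cost is a rerun of an existing simulation and a few lines of text. No extra participants are needed and trial conduct does not change. The stated power may become slightly less favourable.

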Support for peer mentors. We also will take precautions to decrease risk of emotional distress for peer mentors. These precautions include the following: 1) enroll peer mentors who have 5 or more years in recovery, 2) provide regular weekly supervision and monitor the health of the peers, and 3) encourage mutual support among peer mentors in the study. We will aim to recruit peer mentors who are at low risk of relapse, which we will be determined by length of time in recovery and level of function, such as ability to volunteer, engage in community activities or paid employment. Training will reinforce that peer mentors are not clinicians, are not expected to be clinically responsible for depressed older adults, and that their role is one of informal psychosocial support. The social worker who is the supervising mental health professional will regularly monitor the peer mentor's emotional well-being and address any signs of distress. If any peer mentor expresses emotional distress or the social worker detects signs during supervisory meetings such as irregular attendance and role performance, the social worker will discuss and provide support to the peer mentor. If the peer mentor experiences depression that rises to the level of clinical depression, the social worker will ensure that the peer is receiving clinical care, will discuss with the peer whether continued participation in the study is feasible and may conclude that a peer's participation in the study should be suspended until the peer's depression is no longer clinically significant.

The approach of the supervising professional will be to accommodate the needs of peer mentors in their role, e.g. Non-clinical, psychosocial support role. Supervisory meetings will also encourage mutual support among peer mentors in the study. Finally, qualitative studies of peers suggest that peers benefit positively from being in a helping role, despite concerns about increased vulnerability. We interviewed peer mentors in our preliminary work (pilot study) in which they interacted with depressed older adults, and peer mentors stated that working in a role to help others who are struggling with depression gave their lives purpose, gave them opportunities for continued learning, and contributed to sustaining their own recovery. Our experience is based on a small number of peer mentors but is supported by studies that have shown the benefits of being in helping roles. Peer mentors will be trained to report any expression of self-harm immediately to the Program Coordinator who will enlist the Social Worker and Geriatric Psychiatrist as needed.

c. Plan for reporting unanticipated problems or study deviations.

Although we are not studying experimental drugs, the intervention is experimental with the attendant risks. To address this, we will have a Data and Safety Monitoring Board (DSMB) to monitor the study with an attendant monitoring plan. The role of the DSMB will be to ensure that no unexpected, untoward consequences of the experimental intervention occur, and if they do, to implement safeguards to decrease or eliminate future risks. Although the risk is low, the Peer Program could induce emotional distress associated with discussion of past trauma or current stressors. We will include as serious adverse events acts of suicide or attempted suicide and threats of violence or violence toward the research team, providers or outside personal contacts. Any adverse events related to behavior will be provided to the DSMB in real time. These adverse events include, but are not limited to, suicidality, homicidality, or inappropriate or threatening behavior with the research or clinical staff. Less serious adverse events related to the treatment of depression will be compiled and summarized for the DSMB at their scheduled meetings. All other severe adverse events in participants will be monitored by the Principal Investigator, the Study Coordinator, and the Social Workers and will be reported to the DSMB regardless of a priori expectation or investigator assessment of likelihood of the study being the cause of the adverse event.

The DSMB will also have the power to request further data (e.g. depression outcome data) from the Principal Investigator based on any concerns that may be raised in the ongoing investigation in the scientific community. Interim analyses will be performed and compiled for review by the DSMB. At any time during the study, based on its findings, the DSMB can put the study on either temporary hold or stop the study entirely after notifying the Principal Investigator and the IRB. In the rare case in which they have to do so, the DSMB will generate a formal report to the Principal Investigator, the sponsor (NIMH), and the IRB. This report would then be modified for a lay reader, a

version for past participants and current participants would be produced, and the letter would be sent to all past and current study participants and their referring providers.

The DSMB will first meet 6 months after the first participant is enrolled to review both the non-serious and serious adverse event rates. They will meet annually and also meet on an ad hoc basis if the real time serious adverse events warrant meeting, in their judgment. The format of the meeting will include a presentation of the summarized data by the Principal Investigator and the Biostatistician. The absolute rates of adverse events as well as the rate compared between the intervention and control groups will be presented. After presentation by the study team, the DSMB will be left to confer alone. If deemed to be warranted, as described above, the DSMB can request a temporary hold be placed on the study until further data are reviewed.

- d. Legal risks such as the risks that would be associated with breach of confidentiality.

For older adult participants, risks regarding breach of confidentiality and disclosure of clinical information exist and may be heightened due to use of non-professional peer mentors in the proposed study. Should confidentiality safeguards fail, there is potential harm in the form of social risks and disclosure of private information. However, the risks of participation should be no more than minimal, with effective confidentiality safeguards. The safeguards include the following: 1) Peer mentors will sign a contract of confidentiality agreement before participating in the project, receive confidentiality training and the importance of confidentiality will be stressed throughout training and supervision sessions on a weekly basis. 2) Older adult participants will be informed that absolute confidentiality cannot be guaranteed but study staff will put rigorous procedures in place. In our experience, there were no known breaches of confidentiality in our pilot study, older adults did not express concern about this during the consent process, and none dropped out of the study for this reason. All information collected will be coded with a study identification number and will be stored in locked files that only staff associated with the study can access. These records will be protected by the confidentiality system of Massachusetts General Hospital and will not be disclosed except as required by law. Audio recordings will be saved in Massachusetts General Hospital OneDrive.

- e. Financial risks to the participants.

There are no costs to the participant associated with the study and we do not foresee financial risks to them.

8. Benefits

- a. Description of the probable benefits for the participant and for society.

The proposed study may benefit the older adult participants in terms of psychoeducation and self-care skills associated with depression, monitoring of symptoms and services delivered by a peer mentor who is under a mental health professional's supervision. The peer may benefit from increased sense of self-efficacy in helping another person and will have an increased knowledge base from the mental health training provided by the study. Benefits to society may include new knowledge regarding the provision of mental health services in the community. If the peer program is successful, new ways to provide depression care services in the community setting to low-income minority older adults will be established. The risks to the patient for participating in this project are minimal and the possibility of improving depression care is substantial.

A.4. Importance of knowledge to be gained

This research will inform the development of peer programs whose aim is to improve access and engagement of depression care among minority and low-income populations. Given that minority older adults receive inadequate or no mental health care and are less likely to access traditional mental health services, developing new methods of delivering depression care is important.

9. Payment and Remuneration

- a. Detail compensation for participants including possible total compensation, proposed bonus, and any proposed reductions or penalties for not completing the protocol.

Peer mentors - Each peer will participate in 20 hours of training conducted by the PI and also meet weekly for supervision with the social worker for each contact hour with the client. Peer mentors will be paid \$100 for attending 20 hours of training. They will be only be paid if training is completed and they are successfully matched with a

least 1 depressed older adult participant. Peer mentors will be also paid a total of \$50 for 1 meeting with a client and 1 supervision meeting. For each older adult who will receive 8 meetings with the peer, peer mentors will receive \$400. They will receive an additional \$20 for a post-study interview.

Older adult incentives - Participants will be given a token of appreciation of \$30 with for one (1) baseline assessment meeting, 8 week assessment, 3, 6, 9 and 12 month follow up assessments for total of 6 assessments for a total \$180.

